## **V. STUDY PROCEDURES**

All subjects will have an IV placed and baseline labs sent, as is standard for all patients admitted to the Center for Women and Newborns Labor and Delivery unit. Baseline labs will include: type and screen and complete blood count (CBC).

At the time of delivery, enrolled subjects will be assessed for poor uterine tone despite the administration of oxytocin following delivery. If either methylergonovine or carboprost is requested by the obstetrician or anesthesiologist, subjects will then be randomized by the anesthesiologist to either "methylergonovine" or "carboprost" groups by a computer generated randomization scheme printed on a piece of paper in a sealed envelope. The anesthesiologist will then withdraw the appointed medication (based on subject randomization) from the O.R. omnichannel and administer it without revealing to anyone in the O.R. which drug was given. They will document the medication in the subject's Epic record in the usual fashion.

The obstetrician and nurse, involved in the cases as well as the study investigator will be blinded to the study group assignments. All physician co-investigators (with the exception of the principal investigator) and the statistician will be blinded to study group assignments throughout the study. As such, these co-investigators will not be involved in the obstetric care of the study subjects, with the following one exception: Every effort will be made to keep the study investigator who consented the subject out of the operating room and uninformed in the subject's clinical care in all cases. However occasionally, due to staffing challenges and clinical acuity of a patient's case (e.g. massive hemorrhage), the anesthesiology attending or fellow who consented the patient may need to be involved in the patient's intraoperative or postoperative care. To minimize any chance of patient coercion and bias in clinical decision-making, the consent process will occur first with the study investigator anesthesiologist. Only after consent is complete and the patient enrolled will the same anesthesiologist who consented the patient end up caring for the patient. This scenario will only occur in situations when a staffing shortage occurs or the case requires additional help due to a life-threatening situation. Everything possible will be done to avoid that situation. Thus the patient will agree to participate in the study in advance of forming any physician-patient relationship with the study investigator, and the study investigator will only affect clinical care as a helper in case of clinical necessity, not as the leader of clinical decision-making (i.e. the study investigator will not be the primary anesthesiologist of record for the case).

The study drug will consist of either:

1. 0.2mg methylergonovine, or
2. 0.25mg 15-methyl prostaglandin F2a

The anesthesiologist will administer the study medication in a 1mL syringe intramuscularly in the patient's deltoid muscle. Each patient will have both medications available in the fridge where hemorrhage medications are stored, so that the second of the 2 drugs can be easily administered in succession if an additional agent is needed.

At the time of administration of the first study drug, the anesthesiologist will ask the obstetrician to rate the uterine tone on a scale of 0 to 10 (0 being 'no tone', 10 being 'excellent tone'). The anesthesiologist will then set a timer. After administration of the study drug, patient care will receive our usual standard of care. At 5 and 10 minutes from the onset of timing, the anesthesiologist will once again ask the obstetrician for a rating of uterine tone between 0 and 10. These values will be recorded by the anesthesiologist on a Uterine Tone Score Intraop Data Collection sheet included in the sealed envelope provided by the investigator.

If an additional uterotonic agent is requested by the obstetrician, the unblinded anesthesiologist will prepare the other drug, again in a-1mL syringe. Timing of this administration will be noted on the study record sheet. All other medications and interventions will proceed as usual and in an unblinded fashion.; If uterine tone remains unsatisfactory, identity of the study drugs will remain blinded, if possible. Any repeat administrations of carboprost or methylergonovine will be given by the anesthesiologist based on the timing of administration of the 2nd study drug.

The obstetric physicians and nurses caring for the patient will document quantitatively measured blood loss during the delivery. The volume of blood mixed with amniotic fluid in the graduated suction jars and the number of sponges soaked with blood will be noted. In addition to baseline serum hematocrit, postpartum serum hematocrit and platelet count, will be evaluated on the first postoperative day after C/S. The change in serum hematocrit will be compared among study groups.

At the end of the C/S, the anesthesiologist will complete the Randomization Sheet, documenting the patient MRN and study ID number. They will return the Randomization sheet and the Uterine Tone Score Intraop Data Collection sheet in the [previously sealed] envelope to a locked room on L&D where all paper documents for the study will be temporarily stored until the unblinded principal investigator collects the sheets (on the same day as subject enrollment) and brings them to a locked filing cabinet in a locked office to which only the principal investigator has access.

Within the first 24 hours after delivery, but no sooner than the time of patient transfer from the labor and delivery floor to the postpartum unit, Between 2-4 hours postpartum and again between 18-24 hours postpartum, a blinded study investigator who is not involved in the subject's clinical care will interview the patient by phone (to avoid physical contact and minimize the risk for COVID-10 transmission) and record the information from the interview on the corresponding '2-4 Hr Interview Guide' or '18-24 Hr Interview Guide'. This will allow them to assess subjective side effects of the study medication such as G.I. upset, dizziness, shortness of breath, palpitations or chest pain. Non-English speaking patients will be interviewed in person with the assistance of an in-person interpreter from BWH Interpreter Services.

Subject randomization, patient MRN and the linked study ID number will be documented on a separate form in the secure electronic database, REDCap database by the unblinded principal investigator. This form will be visible only to the principal investigator. An unblinded study investigator (i.e. the principal investigator, or a research assistant, when one is hired in the future) with access to REDCap will be responsible for collecting and entering all primary and secondary outcomes from the Uterine Tone Score Intraop Data Collection sheet, the 2-4 Hour Interview Guide and the 18-24 Hour Interview Guide and Epic medical records (including side-effects of study medications) into REDCap. Subject randomization will be documented, on a separate form in the database to which only the principal investigator has access, in order to preserve the integrity of the data collection and entry.

The need for blood product administration and quantity of each component given within 24hrs after cesarean section will be recorded. In addition, the investigator will record any additional interventions performed to halt bleeding, such as Bakri balloon placement, B-Lynch sutures, uterine artery embolization or hysterectomy.

Total intravenous fluids given from start to conclusion of the delivery will be recorded. The use of vasopressors, uterotonic agents, anti-emetic agents will be recorded. Length of stay and any postoperative complications occurring during the hospital stay will be documented at the time of hospital discharge.

All clinical and other data obtained during this study will be considered confidential. Procedures to limit access to subject charts and information from the study will be in place. Study participant data will be de-

identified upon entry into the data collection tool and will be known only to the investigators. No information regarding the identity of individual subjects will be utilized for publications.

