## **VII. RISKS AND DISCOMFORTS**

Adverse reactions to methylergonovine include increased blood pressure, seizure, dizziness and headache, and nausea, vomiting, diarrhea and abdominal pain from uterine contractions. Rare effects include chest pain, myocardial infarction, coronary vasospasm, tachycardia, dyspnea, and hematuria. A large retrospective study of over 2 million parturients found no significantly increased risk of acute coronary syndrome or acute myocardial infarction after receiving methylergonovine. ACOG recommendations nonetheless state that methylergonovine should be avoided in patients with hypertension and cardiovascular disease.

The most common adverse reactions to carboprost include nausea, vomiting, diarrhea, as well as headache, myalgias, increased temperature and flushing. Due to its stimulation of smooth muscle contraction, modest increases in blood pressure may be seen, but these are generally clinically insignificant. Additionally, bronchospasm, abnormal ventilation-perfusion and hypoxia may occur, and may be particularly severe in patients susceptible to these complications. Carboprost is therefore contraindicated in patients with active asthma.

Patients with any contraindication to either of the study drugs will be excluded from participation in the study. Patients with a diagnosis of asthma will be interviewed to confirm if their asthma is active. Any patient who has used a bronchodilator within the past 24 months will be considered to have active asthma and will be excluded. If a patient carries a diagnosis of 'childhood asthma' and/or has not needed a bronchodilator for >24 months, they will be considered eligible to participate in the study. After enrollment, patients will be evaluated for all of the above side effects by a clinical investigator between at time of transfer to the postpartum floor and again between 18 to 24 hours after delivery. The obstetric 6-

week postpartum follow-up record will be reviewed by a clinical investigator to screen for thrombotic events or other side effects.

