At the end of the C/S, the anesthesiologist will return the Randomization sheet and the Uterine Tone Score Intraop Data Collection sheet in the previously sealed envelope to a folder where all paper documents for the study are temporarily stored in a locked room on the L&D floor. On each day of subject enrollment, the unblinded principal investigator will collect the envelope with the Randomization sheet and Uterine Tone Score Intraop Data Collection sheet and transfer it to a locked filing cabinet in a locked office to which only the principal investigator has access.

After the subject has recovered on the L&D floor and is ready for transfer to the postpartum floor, a blinded study co-investigator will interview the patient by phone (to limit physical contact, due to COVID-19 precautions)

using the '2-4 Hour Interview Guide'. At 18-24 hours postpartum, the subject will again be interviewed by phone by a blinded study co-investigator, using the '18-24 Hour Interview Guide'. Both postpartum interview guides will contain the same content, allowing for subjective adverse effects to be accurately assessed at 2 timepoints. (no later than 24 hours after delivery). This data will be documented on the 2-4 Hour and 18-24 Hour Interview Guides, to be retrieved by the principal investigator (who is not blinded) after the day of subject enrollment, then stored in the locked office, and ultimately entered into a secure electronic database, REDCap, by a blinded study investigator. This will allow them to assess for any subjective side effects of the study medication, as listed below (Secondary Endpoint #9).

An unblinded study investigator not involved in data collection and with access to REDCap will be responsible for collecting all primary and secondary outcomes (including side-effects of study medications) from the Uterine Tone Score Intraop Data Collection sheet, the Pre Transfer Interview Guide and Epic medical records onto the Second Line Uterotonics Data Collection Sheet and entering this information into REDCap. Subject randomization, patient MRN and the linked study ID number will be documented on a separate form in the REDCap database by the unblinded principal investigator, to preserve the integrity of the data collection and entry.

Study endpoints will be:

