## **FORESEEABLE RISKS AND DISCOMFORTS**

Provide a brief description of any foreseeable risks and discomforts to subjects. Include those related to drugs/devices/procedures being studied and/or administered/Performed solely for research purposes. In addition, include psychosocial risks, and risks related to privacy and confidentiality. When applicable, describe risks to a developing fetus or nursing infant.

As described above, all patients will be treated with the standard of care and should therefore not be exposed to any additional risk or discomfort. As is typical practice, all patients will receive an intravenous (IV) line and baseline labs on admission to the L&D floor, and oxytocin will be given immediately after the baby is delivered and the cord clamped. Thereafter, patients will receive all usual measures to manage postpartum bleeding, including, but not limited to, administration of additional uterotronics, uterine massage, additional diagnostic lab values and resuscitative measures. Second-line uterotronics will be given as per study protocol, with additional uterotronics as per clinical assessment.

After the delivery, the patient will be monitored on the labor and delivery floor for several hours postoperatively before discharge to the postpartum recovery unit, as is customary.

Only clinical providers will be involved in the care of the patient. Study staff will be involved in consent and collection of data points during enrollment, but they will not participate directly in patient care. Privacy and confidentiality will be maintained as per HIPAA standards.

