All continuous secondary outcomes were initially assessed for the normality of residuals from a multivariable linear regression model with trial site and baseline uterine tone as covariates. Outcomes displaying normally distributed model residuals were analyzed using multivariable linear regression, with effect size presented as adjusted difference in means with 95% CI. Outcomes with all non-zero values that displayed skewed linear regression model residuals were natural log-transformed and analyzed using multivariable linear regression, with effect size presented as adjusted ratio of geometric means with 95% CI. Outcomes containing at least one zero value that presented skewed linear regression model residuals were compared between groups using multivariable quantile regression, with effect size presented as adjusted difference in medians with 95% CI.

All binary outcomes were initially considered for comparison using multivariable logistic regression (for single measurements) or generalized estimating equations with a logit link (for repeated measurements) with trial site and baseline uterine tone as covariates. If the multivariable regression converged, effect size was presented as adjusted odds ratios with 95% CI. If the model did not converge due to low incidence, groups were compared using a Fisher's exact test and effect size presented as risk difference with exact 95% CI.

Time to receive second study drug was compared between groups using a multivariable Cox proportional hazards model, with effect size presented as adjusted hazard ratio with exact 95% CI. Complete-case analysis was performed for all secondary outcomes. All analyses were performed using SAS software version 9.4 (SAS Institute, Cary, NC).

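### The first symptom interview is tied both to 2–4 hours postpartum and to transfer off labor and delivery, so its timing and completeness depend on recovery

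*Protocol*

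**What the plan says.** The Detailed Protocol, section V (Study Procedures), times the blinded interviews in one run-on sentence. It opens with an outer limit and a floor, "Within the first 24 hours after delivery, but no sooner than the time of patient transfer from the labor and delivery floor", and continues with two clock windows, "Between 2-4 hours postpartum and again between 18-24 hours postpartum, a blinded study investigator who is not involved in the subject's clinical care". The floor and the first window meet without a break: "but no sooner than the time of patient transfer from the labor and delivery floor to the postpartum unit, Between 2-4 hours postpartum". The interviews are by phone; the in-person route is only for non-English-speaking women, with an interpreter.

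Two other places time the first interview differently:

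- Protocol Summary, Research Design and Methods: "After the subject has recovered on the L&D floor and is ready for transfer to the postpartum floor", using the 2–4 hour guide.
- Detailed Protocol, section VII (Risks and Discomforts): "between at time of transfer to the postpartum floor and again between 18 to 24 hours after delivery".

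On the expected stay, the Protocol Summary (Foreseeable Risks and Discomforts) says only that "the patient will be monitored on the labor and delivery floor for several hours postoperatively".

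The symptom endpoint has a fixed clock period, the first 2 hours postpartum (section II, secondary outcome j; Protocol Summary, secondary endpoint 9). Both printed interview guides instead ask about symptoms up to transfer to the postpartum floor. For missing data the SAP states: "Complete-case analysis was performed for all secondary outcomes".

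**The concern.** Transfer off labor and delivery happens after randomization and reflects how the woman is doing. A woman who is still bleeding, has needed the second drug or has a complication may stay longer or go to intensive care. If the first interview may not precede transfer, when it is held, and perhaps whether it is held, follows her recovery, and recovery may depend on the assigned drug.

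At stake is the tolerability comparison of two drugs whose side effects the protocol itself describes as different. If one arm has more late transfers, its symptom reports would cover a longer period. If some of those interviews are missed, that arm would lose women who may be more symptomatic. The primary outcome, uterine tone at 10 minutes, is untouched.

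**Working it through.** The documents give no figure on this point, so there is none to reproduce. The check sets the texts side by side, then gives an illustration on assumed inputs.

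1. **Is there always a permitted time?** Let T be the time of transfer in hours after delivery. Under section V the first interview may run from max(2, T) to 4 hours. With T = 3 that is 3 to 4 hours. With T = 5 it would have to start at 5 and end by 4, so no time is permitted. The interval is empty whenever T is above 4, or when the woman goes to intensive care and does not reach the postpartum unit in time. The stay on labor and delivery is counted from the end of surgery, while the window is counted from delivery, so the rest of the operation also uses up the window.

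2. **Do the other texts settle it?** No. Section VII puts the interview at transfer and states no 4-hour limit. The Summary puts it at readiness for transfer, which precedes transfer and so comes before section V allows it, yet on a form named for 2–4 hours. In all three places the timing follows recovery.

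3. **What does a late interview measure?** The guides ask about the period up to transfer, which is T hours long; the endpoint covers 2 hours. With T = 3 the answer covers 3 − 2 = 1 hour beyond the endpoint; with T = 6 it covers 6 − 2 = 4 hours beyond. Slower recovery means a longer symptom period.

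4. **What does the complete-case rule remove?** Missing values only. A late answer is a recorded answer, and neither document sets it to missing. Only an interview that was not held is lost.

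5. **How large could the loss be?** All inputs are assumptions: 5% of one arm and 15% of the other are transferred late (m); symptom rates are r = 50–60% in late women and 30% in the others.
   - True rate = (1 − m) × 0.30 + m × r.
   - m = 5%: 0.285 + 0.025 = 31.0% to 0.285 + 0.030 = 31.5%.
   - m = 15%: 0.255 + 0.075 = 33.0% to 0.255 + 0.090 = 34.5%.
   - If every late woman is missed, both arms read 30%, and a true difference of 2.0 to 3.0 points is hidden.
   - If half are missed, observed rate = [(1 − m) × 0.30 + 0.5 × m × r] / (1 − 0.5 × m). At r = 60%: 0.300/0.975 = 30.8% against 0.300/0.925 = 32.4%, a difference of about 1.7 points instead of 3.0. At r = 50%: 0.2975/0.975 = 30.5% against 0.2925/0.925 = 31.6%, about 1.1 instead of 2.0.
   - If all are interviewed late, nothing is lost, and only the longer recall period of step 3 remains.
   - With equal loss of 5–10% in both arms, true rates of 31–33% read as 30%, an understatement of 1–3 points.

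6. **Against what noise?** With 50 women per arm and rates near 30%, the standard error of a difference is √(2 × 0.3 × 0.7 / 50) = 0.092, about 9 points.

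**The case against.** The strongest reply is that this is a drafting slip. The capital letter in mid-sentence suggests an older single-interview rule left beside its replacement, and the Summary's use of the 2–4 hour guide at readiness for transfer suggests that the team took 2–4 hours as the usual transfer time. A stay of several hours does not show stays beyond 4 hours. The second interview has the same content, side effects are also taken from Epic, and if the two interviews are analyzed as repeated binary measures by GEE, one observed interview keeps a woman in the model.

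Most of this limits the consequence without removing the conflict. The 18–24 hour interview asks about the same pre-transfer period, but many hours later, and the transfer floor can be read as governing it too. Epic entries are collected by an unblinded investigator, whereas the interview is blinded. The SAP does not say that symptoms are modeled as repeated measures. If they are, GEE is generally unbiased only when missingness is unrelated to the symptom given the covariates, here site and baseline tone. Multiple imputation is planned only for uterine tone.

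A reader might infer that every woman still on labor and delivery at 4 hours is dropped by the complete-case rule, so that the arm that fails more often looks better tolerated. The documents do not support that. No rule voids a late interview, and nothing shows how many women stay beyond 4 hours, that stay differs by arm, or that late women would be missed.

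**Conclusion.** The conflict stands. Section V leaves no permitted time for the first interview when transfer comes after 4 hours, and the other two texts tie the interview to transfer or readiness for it. Timing and completeness therefore depend on recovery after randomization, while the endpoint is fixed at 2 hours postpartum. The likely effects are a longer symptom period for late women and some missed first interviews.

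The size of any bias cannot be derived from the documents. The 2–3 points above need assumed shares, assumed symptom rates and the loss of every late woman; they are an outer illustration, well inside the standard error. The bias is probably small and confined to secondary tolerability outcomes. The point still merits a change, because the rule is explicit, it ties ascertainment to a post-randomization event, and it can be removed by wording.

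**What to change.** - **Section V:** delete the condition that the interview may not precede transfer.
- **Section VII and Protocol Summary:** align both, so that the first interview is by phone at 2–4 hours postpartum wherever the woman is, or in person with an interpreter where section V already provides for it.
- **Interview guides:** replace the question about the period before transfer with the endpoint's period, the first 2 hours postpartum. Without this, a woman interviewed on labor and delivery would be asked about a period that has not ended.
- **Records:** note the actual time of each interview.
- **SAP:** state that late first interviews stay in the analysis, and report late and missed first interviews by arm.

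The cost is wording plus one recorded time, with the same interviewers and the same number of calls. The downside is that some calls will reach women still recovering on labor and delivery. The SAP is written in the past tense; if the interviews are already complete, the last item can still be done as far as interview times were recorded, and both guides have a field for them.
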